8.6. Withdrawal Criteria

In accordance with the Declaration of Helsinki, human patients have the right to withdraw from the study at any time for any reason. The investigator and Tonix also have the right to remove patients from the study. Additional information regarding withdrawal or discontinuation of patients is described in detail in [Section 10.5.1](#).

9. STUDY DRUG MATERIALS AND MANAGEMENT

9.1. Study Drug Packaging, and Labeling and Storage

Study drug supplies will be packaged identically so as to maintain the integrity of the study blind. The study medication bottles will be labeled minimally with the following information: study number TNX-CY-P302, sponsor name and address, bottle number, quantity, storage conditions, usage instructions, and caution statements for investigational new drug, i.e., Caution: New Drug – Limited by United States Law to Investigational Use, and Keep Out of Reach of Children and Pets.

Each study medication bottle will contain 40 tablets. Two bottles will be dispensed to each patient at Visit 2 (baseline), Visit 4 (Week 4), and Visit 5 (Week 8); this will provide the patient with 80 tablets to cover the 4 weeks of dosing between visits, plus additional tablets to cover loss and/or visit window variability. The patient should be instructed to take all the tablets in one bottle before opening the second bottle. The patient should be instructed to keep this study medication in a safe location out of extreme environmental conditions and out of the reach of children and pets, and be instructed that this medication is not to be taken by any individual other than the study patient. Each patient will also be instructed that they will be expected to return both bottles and all unused study medication at each clinic visit; unused medication will be counted to assess compliance with study drug treatment.

Storage of the study drug at the investigational site should be under locked and secure conditions with limited staff access. Study drug should be stored at 20-25°C/68-77°F in a temperature/humidity-monitored room; however, brief excursions (15-30°C/59-86°F) as defined in the Study Reference Manual (IP Receipt and Storage) are permitted without the sponsor's approval.

9.2. Dosing Instructions

Patients will be instructed to take two tablets of their assigned study drug (TNX-102 SL 2.8 mg tablets or placebo tablets) sublingually, placed simultaneously under the tongue, each evening at bedtime starting at bedtime on evening of Day 1 (Day of Visit 2) and continuing without interruption for 12 weeks. The study drug should be taken at bedtime after teeth brushing and other oral care has been completed. The mouth/sublingual area should be moist at the time of dosing, so the patient should drink a few sips of water prior to dosing, especially if prone to dry mouth. Patients will be instructed to place the two SL tablets under their tongue and keep them there until they have dissolved. They should not swallow, crush or chew the tablets. Patients should not eat or drink (or chew gum) for at least 15 minutes after dosing, and preferably not until morning. Patients will be reminded that only 2 (two) tablets are allowed per day. Note: In the event that the patient misses a dose, instruct the patient to continue dosing with two (2) tablets the next evening; i.e., they should not take more to make up for the missed dose.

9.3. Dispensing Instructions

Each patient who has met the randomization criteria (Section 8.3) will be assigned 2 double-blind treatment bottles at Visit 2 via the IWRS, with a unique, but otherwise random bottle number that is generated when the study coordinator successfully completes randomization procedures. Patients will also be assigned two new treatment bottles at Visits 4 and 5 via the IWRS. The bottle numbers provided by the Interactive Web Response (IWR) system at these visits will tell the site which treatment bottles have been assigned to the patient.

In the event of loss of study medication, new medication will be provided by the IWR system, when appropriately requested by the site and/or the sponsor or designee.

Study treatments for the double-blind treatment phase are either:

Treatment A: 2 × TNX-102 SL 2.8 mg tablets ("TNX-102 SL") to be taken sublingually once daily at bedtime.

Treatment B: 2 x placebo tablets (“placebo”) to be taken sublingually once daily at bedtime.

9.4. Release of Clinical Study Supplies to the Investigator

Tonix or Tonix’s designee’s standard operating procedures for releasing clinical trial supplies to the site will be followed.

9.5. Study Drug Accountability and Reconciliation

All patients will be expected to bring their bottles of study medication with them to all study visits. At each study visit, the site staff will inspect the medication bottles, and perform a count of the tablets remaining in the bottles and document this in the patient’s record. An assessment of medication adherence should be done by the study staff to ensure that the patient understands all dosing instructions and is taking the medication as prescribed. Patients will be asked for an explanation if the count of returned study drug tablets indicates a discrepancy between the expected number of tablets dosed and the number returned in the bottles. If it is found that the patient is not taking the study medication as expected, the patient will be re-c counseled with instructions, and this should be noted in the patients’ records. A deviation should be recorded on any patient who is less than 70% compliant with dosing between visits.

If the patient fails to return any of the unused study drug as expected, the patient should be questioned regarding the reason for the lower than expected tablet number and about potential misuse, abuse or diversion. If more than 8 tablets cannot be accounted for at any of the visits where drug is returned (Week 4, 8 and 12), the investigator will be asked to evaluate the situation, and a written summary of this evaluation should be added to the source and entered onto the case report form (CRF). Situations where replacement drug is requested, or when more than 8 tablets cannot be accounted for, should be recorded as deviations.

All study medication, including partial and empty bottles, must be maintained at the study site until Tonix or its designee verifies drug accountability and provides instruction for destruction or the return of the investigational product to the Sponsor’s drug distribution depot.

Tonix or their designee will perform drug accountability which entails reconciliation between the amount of drug shipped to the study site, study drug assigned and dispensed to the patient (including returned unused assigned study drug), and study supplies that were never dispensed and/or assigned to patients.

10. STUDY VISITS AND PROCEDURES

The overall and detailed schedule for study procedures and visits is provided in [Appendix 1](#).

10.1. Visit 1 (Screening: Day -21 to -7)

10.1.1. Informed Consent

Before the potential patient has undergone any study-related screening procedures, including any downward titration or withdrawal of medications, the nature of the study and the potential risks associated with it will be explained to the patient, and the patient will be given an opportunity to ask questions to his or her satisfaction. After all questions are answered, but before proceeding further, the patient must read and sign a written informed consent form. This signed informed consent form will be retained in the Investigator's study file, and the date the patient signed the form will be entered into the Case Report Form (CRF). The patient will be provided with a copy of his or her signed and dated informed consent form. The patient will be required to sign all updated informed consents.

Separate written, signed informed consent must be obtained if the patient is to participate in the optional pharmacogenomic assessment.

10.1.2. Screening Overview

Screening Visit 1 will start a variable length screening period. The length of the screening period is to be no shorter than 7 days, but may be as long as 21 days in order to accommodate medication taper and discontinuation or other study requirements.

If the patient is eligible to continue in the study, and does not need to discontinue any excluded medication, the patient may be scheduled to return for Visit 2 (Randomization) in 7 (or more) days, assuming all screening evaluations have been completed, including confirmation of acceptable laboratory and ECG results. If the patient needs to undergo taper and discontinuation of excluded medication, the Investigator will generate a written down titration schedule for the patient and will schedule Visit 2 such that the date of Visit 2 is at least 1 week after the date of the final dose of any excluded medication. If additional clinic visits are deemed necessary by the investigator for clinical monitoring of the patient before scheduling Visit 2, such visits will be recorded as unscheduled visits.

10.1.3. Patient Numbering

All screened patients will be assigned a unique concatenated 6-digit site-patient number (e.g., 202-012) by the IWR system. A screening log or system documenting the following information will be recorded and maintained, and will include the patient's initials, screening number, whether the patient was ultimately randomized or not, and if not randomized, the reason the patient was excluded/screen-failed.

10.1.4. Screening and Assessments/Procedures

The following screening assessments/procedures will be completed in the following general order:

- Obtain written informed consent to participate
- Obtain demographics, including alcohol, nicotine/tobacco (smoking and/or chewing), and marijuana use
- Obtain medical history
- Obtain prior and current medication history, including all prior PTSD therapies and other treatments for psychiatric indications
- Obtain psychiatric history
 - Mini International Neuropsychiatric Interview (M.I.N.I. 7.0.2)
 - McLean Screening Instrument for Borderline Personality Disorder (MSI-BPD)
- Administer PTSD Rating Scales:
 - Life Events Checklist (LEC-5)
 - Criterion A – Assessment Form (CA-AF)
 - Clinician Administered PTSD Scale (CAPS-5) (Since Last Month version)
- Perform physical examination, including visual inspection of the oral cavity (including floor of mouth/sublingual area)
- Obtain vital signs, height, weight and BMI
- Draw samples for clinical laboratory tests for:
 - Chemistry, hematology, HIV and TSH, with free thyroxine also performed if TSH is outside the upper or lower limits of normal
 - Urine Drug Screen (central laboratory)
 - Serum pregnancy test (for women of child-bearing potential)
- Conduct 12-lead electrocardiogram
- Administer Depression/Suicidality Scales
 - Montgomery-Åsberg Depression Rating Scale (MADRS)
 - Columbia Suicide Severity Rating Scale (C-SSRS, Baseline/Screening Version,)
- Review inclusion/exclusion criteria

Only those patients meeting all of the inclusion and none of the exclusion criteria will be eligible to continue. NOTE: Final determination of eligibility based on clinical laboratory tests will be made when results have been returned.

Sites will be asked to complete and submit to the Tonix medical monitoring team key screening information. This information will be reviewed by the Tonix medical monitoring team to help ensure the selection of well-qualified patients. The specific requirements and timelines associated with this pre-randomization review process will be outlined in a separate document.

Once eligibility has been confirmed and authorization for randomization granted by a Tonix medical monitor, eligible patients will return to the clinic for Visit 2.

There is no requirement for Follow-Up visits for patients who are screen failures. Patients who fail to qualify should have their medication adjusted, as appropriate, per the judgment of the Investigator and be released from the clinic. There will be no requirement to enter data into the electronic case report form (eCRF) for patients who are not randomized.

10.2. Visit 2 (Baseline: Day 1)

Visit 2 should be scheduled 7 to 21 days after Visit 1. Study procedures will be completed (including qualifying baseline assessments for the C-SSRS and CAPS-5). If the patient meets all randomization criteria, the patient will be randomized via the IWR system to receive double-blind study medication.

10.2.1. Pre-Randomization Assessments

The following assessments must be completed at Visit 2 to confirm that the patient is eligible for randomization. Upon arrival at the clinic, the following assessments should be done, in the following general order:

- Assess occurrence of adverse events
- Update medical history (with changes since screening noted)
- Assess changes in medication history and concomitant medications
- Obtain vital signs and weight
- Administer CAPS-5 - “Symptom Severity Version”, using 1-week recall
- Conduct urine drug screen (urine dipstick, only as necessary, if select Visit 1 tests were positive for excluded medications that required discontinuation prior to randomization)
- Conduct urine pregnancy test (for women of child-bearing potential)
- Perform visual examination of the oral cavity
- Have the patient complete the following outcome scales (in order):
 - SDS
 - PROMIS scale for sleep disturbance
 - CSFQ-14
- Administer the MADRS
- Administer the C-SSRS- Since Last Visit Version
- Physician to assess CGI-S (needs to be completed once all other assessments are available for investigator to review)

10.2.2. Randomization Criteria

Once all pre-randomization assessments have been completed, only those patients who meet all of the following randomization criteria will be eligible to continue:

1. Patient continues to meet all inclusion and exclusion criteria, including urine and blood test results, and
2. Visit 2 total CAPS-5 score ≥ 33 (“Symptom Severity” version using 1-week recall), and
3. No active suicidal intent or plan, or suicidal behavior, based on Investigator’s judgment, and Visit 2 C-SSRS responses (e.g., no C-SSRS Type 4-5 ideation or suicidal behavior since Visit 1) and/or a score of > 4 on Item 10 of the Visit 2 MADRS.

If the patient does not satisfy these randomization criteria, the patient has failed to qualify for this study and should be considered a screen failure, with the reason documented. With Medical Monitor approval, if the patient is otherwise considered a qualified and compliant patient, Visit 2 may be delayed to accommodate situations in which extenuating or short-term circumstances do not warrant screen failure.

If the patient does satisfy these randomization criteria, then continue with the following:

- Randomize the patient via IWRS Randomization System
- Dispense 4-week supply (two bottles) of double-blind study medication
- Review patient instructions regarding study drug dosing ([Section 9.2](#))
- Schedule next study visit

10.3. Visit 3 (Telephone Visit: Day 14)

Visit 3 will be done as a telephone call to the patient and should be conducted after 2 weeks of treatment, on Day 14 ± 3 days.

The following steps should be completed:

- Assess changes in concomitant medications
- Assess study drug compliance based on patient verbal report
- Assess occurrence of adverse events, including any oral adverse events and whether an unscheduled visit is indicated for an examination of the oral cavity
- Review patient instructions regarding drug dosing.
- Administer the ‘Since Last Visit’ C-SSRS

After all of the items have been reviewed with the patient, the patient should be given an appointment to return to the clinic for Visit 4, and be re-instructed, as necessary, on dosing instructions, and reminded to bring study medication back to the clinic at their next visit.

10.4. Visit 4 and 5 (Weeks 4 through 8)

Visits 4 and 5 are similar study visits that are scheduled to be conducted after 4 and 8 weeks of treatment, respectively. Visit 4 should occur on Day 28 ± 5 days and Visit 5 should occur on Day 56 ± 5 days.

The following assessments and procedures are scheduled for these visits in the following general order:

- Collect study drug and assess compliance
- Assess occurrence of adverse events
- Update concomitant medications
- Obtain vital signs and weight
- Administer CAPS-5-“Symptom Severity Version” using 1-week recall
- Conduct urine pregnancy test (for women of child-bearing potential)
- Have the patient complete the following outcome scales (in order):
 - SDS
 - PROMIS scale for sleep disturbance
 - PGIC
- Administer the MADRS
- Administer C-SSRS - Since Last Visit Version
- Physician to assess CGI-S and CGI-I (needs to be completed once all other assessments are available for investigator to review)
- Dispense new bottles of double-blind study medication as assigned by IWRS

After all of the assessments at each visit have been completed, the patient should be given an appointment to return to the clinic for the next scheduled visit, and be re-instructed, as necessary, on dosing instructions, and reminded to bring study medication back to the clinic at their next visit.

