Investigator, this usage will not interfere with the patient's ability to complete the study or provide reliable data. Information related to marijuana and alcohol use will be collected at Screening.

Patients suffering from depression are eligible for the study, provided their depression does not pose an undue risk to their well-being (e.g., high suicidal risk) or of a severity warranting treatment with antidepressants or other excluded treatments. The investigator will evaluate each patient's medical and psychiatric history, current symptomatology, and the results of the M.I.N.I 7.0.2, MADRS, C-SSRS, and CAPS-5 from Visits 1 and 2, to determine whether it is appropriate for the patient to participate in the study. Patients scoring >26 on the screening MADRS who the Investigator thinks appropriate for randomization will undergo Medical Monitor pre-randomization review to ensure agreement with the investigator's assessment.

Patients with evidence of hepatic impairment secondary to hepatitis B or C at screening, or who are undergoing treatment for hepatitis, should be excluded. Patients with stable and asymptomatic disease whose hepatic enzymes (aspartate aminotransferase [AST] or alanine aminotransferase [ALT]) satisfy the study's entry criteria (< 3 times the upper limits of normal), may be allowed to proceed with randomization with prior Medical Monitor approval.

CAPS-5, M.I.N.I. 7.0.2 and Columbia Suicide Severity Rating Scale (C-SSRS) interviews will be conducted by an approved and qualified individual(s) at each site who has successfully completed training on each instrument.

If a patient scores a 2 or 3 on the suicidal ideation section of the C-SSRS at any visit (including the Screening visit), the investigator and patient should work together to implement a Safety Planning Intervention (SPI). As described in detail in [Section 11.3.3](#), the recommended SPI for this study is the plan developed by [name] and [name] which has been adopted by the U.S. Veteran's Administration (VA) ([Stanley & Brown, 2012](#)). The SPI is a brief clinical intervention aimed at mitigating suicide risk. It consists of a written, prioritized list of coping strategies and sources of support that patients can use to alleviate a suicidal crisis. Sites may use an internally-developed SPI if similar in scope and purpose to the SPI adopted by the VA.

The study timeline and events schedule is provided in [Appendix 1](#).

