11.2. Efficacy Assessments

The primary efficacy endpoint and many of the secondary and exploratory efficacy endpoints in this study are derived from clinician-administered assessments which must be administered by qualified and trained individuals at each clinical site. Study specific training will be required before staff is allowed to administer these scales. In an attempt to minimize variability in responses of a given patient over time, it is important that the same rater administer the scales to a given patient throughout the study unless absolutely unavoidable due to the rater's absence from the clinic. It is also important that the assessments, including those that are patient-completed, be conducted in the specified order, according to specific instructions, and in a setting where the patient has minimal distractions, appropriate privacy and sufficient time to complete them.

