The LEC-5, which documents the patient's lifetime traumatic experiences, will be completed by the patient at Screening Visit 1 before the clinician administered CAPS-5 (Weathers et al, 2013). The CAPS-5 rater will be responsible for reviewing the answers on this form with the patient as part of the completion of the CAPS-5 Criterion A - Assessment Form (CA-AF) in order to determine if the traumatic experience qualifies the patient for inclusion in the study. NOTE: If worst month lifetime PTSD symptoms resulted from earlier trauma(s), such as trauma(s) before age 18 or trauma(s) occurring >9 years prior to screening, the prospective patient should be excluded from participation.

At Screening, the total CAPS-5 score (Diagnostic version with 1-month recall) must be ≥ 29 and must meet the other diagnostic criteria specified in Inclusion Criterion 2 (Section 8.2) in order for the patient to continue. At Baseline (Visit 2), the total CAPS-5 score (past week recall) must be ≥ 33 .

The CAPS-5 interview must be completed by a qualified and trained rater. This rater should be kept consistent for a given patient throughout the study. If circumstances require non-conformity with the single rater approach for any patient, this should be documented. Additional information regarding the conduct, rating, and scoring of the CAPS-5 instrument as well as the requirements for rater training will be provided separately.

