11.3.5. Visual Examination of Oral Cavity

A visual examination of the oral cavity should be done at Screening (Visit 1), Baseline (Visit 2) and after 12 weeks (Visit 6) of treatment and/or at Early Termination. In addition to these regularly scheduled examinations, a visual inspection of the oral cavity (including the sublingual area) should be done any time a patient spontaneously reports an oral adverse event (other than transient sensory AEs such as tongue numbness, tingling or bitter taste) to confirm presence or absence of any irritation or other signs. Additional details related to onset, duration, severity and reversibility of oral events will be documented in the CRF.

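### Adverse events are asked about before the CAPS-5 at every post-dose visit that includes it; reversing the order is a cheap, partial protection for the rater's blind

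*Protocol*

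**What the plan says.** Protocol 10.4 introduces the Week 4 and Week 8 procedures with "The following assessments and procedures are scheduled for these visits in the following general order". The second item is "Assess occurrence of adverse events"; the fifth is "Administer CAPS-5-“Symptom Severity Version” using 1-week recall". Protocol 10.5 (Week 12) and the Protocol 10.5.1 list for early termination on or after Day 11 have the same relative order.

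Protocol 11.2 gives the order some force: "It is also important that the assessments, including those that are patient-completed, be conducted in the specified order".

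On who rates, Protocol 7.1 says the CAPS-5 and two other interviews "will be conducted by an approved and qualified individual(s) at each site who has successfully completed training on each instrument". Protocol 11.2.1 adds, "This rater should be kept consistent for a given patient throughout the study". SAP 3.3 keeps study personnel blinded to study drug but does not mention adverse-event information.

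On the possible cue, Protocol 11.3.5 requires an oral inspection for spontaneously reported oral events, "other than transient sensory AEs such as tongue numbness, tingling or bitter taste". SAP 10.5 has a similar exception for purely sensory events. Protocol 10.5.2 gives oral hypoesthesia as an example, and SAP 10.1 plans a separate summary of oral cavity events.

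**The concern.** The primary endpoint is a score that a clinician assigns after an interview. Blinding protects such a score only while the rater cannot tell which treatment the patient took. A sublingual tablet that numbs or tingles, or tastes bitter, could give the treatment away, and the listed order puts the question that brings out this information shortly before the interview that must not be influenced by it. Because one rater stays with each patient, anything learned at one visit can carry into later ratings.

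If the cue is more frequent on drug and raters expect benefit, the shift would favour the drug. The planned analyses could not remove it: the sensitivity analyses in SAP 9.1.2 vary the handling of missing data and leave the observed ratings as they are.

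**Working it through.** **Step 1. Order of procedures, from the visit lists.**

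| Visit | Adverse events | CAPS-5 | Scheduled oral examination |
|---|---|---|---|
| Weeks 4 and 8 (Protocol 10.4) | item 2 | item 5 | none |
| Week 12 (Protocol 10.5) | item 2 | item 5 | after the CAPS-5 |
| Early termination, Day 11 onward (Protocol 10.5.1) | item 3 | item 6 | after the CAPS-5 |

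Adverse events therefore come first at all four post-dose visit types with a CAPS-5. At early termination the exposure starts sooner: item 1 records the reason for leaving and asks the investigator to weigh adverse events in choosing it. SAP 7.1.2 assigns those early-termination data to the nearest visit window, so they enter the analysis. The baseline visit has the same order but precedes dosing. Early termination before Day 11 has no CAPS-5.

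**Step 2. Separation of roles.** The readable text of both documents has no rule that the rater must differ from the person who takes adverse events, none that withholds adverse-event information from the rater, no central or independent rater, and no check of the blind.

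**Step 3. Size in CAPS-5 points.** The documents give no figure to reproduce. The general form is

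bias = (cue frequency on drug − cue frequency on placebo) × rating shift when the cue is recognised.

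The documents supply neither factor. Assume a 2-point shift and a between-arm difference of 0 to 40 percentage points:

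- 0.00 × 2 = 0
- 0.10 × 2 = 0.2
- 0.20 × 2 = 0.4
- 0.30 × 2 = 0.6
- 0.40 × 2 = 0.8

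The range is 0 to 0.8 points. Only the difference between arms counts; a cue equally common on placebo contributes nothing.

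**Step 4. What a given bias would do to the test.** The planning SD is blacked out, so this step works in SD units and cannot be tied to the points above. Inputs: 125 per arm (Protocol 13.2); at most 120 more patients (SAP 4.1), so (250 + 120)/2 = 185 per arm; two-sided 0.05 (Protocol 13). The level that applies after a sample-size increase is blacked out in SAP 7.1.1.2, so 0.05 is an assumption there. A simple two-sample z-test stands in for the planned model and the stage-wise combination.

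SE = SD × √(2/n): √(2/125) = 0.126 SD and √(2/185) = 0.104 SD.

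False-positive rate with no true effect = 1 − Φ(1.96 − bias/SE) + Φ(−1.96 − bias/SE).

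| Assumed difference in cue frequency | Assumed shift | Bias | Rate, 125 per arm | Rate, 185 per arm |
|---|---|---|---|---|
| 0 points | any | 0 | 0.050 | 0.050 |
| 10 points | 0.10 SD | 0.010 SD | 0.051 | 0.051 |
| 20 points | 0.25 SD | 0.050 SD | 0.068 | 0.077 |
| 30 points | 0.25 SD | 0.075 SD | 0.091 | 0.111 |
| 40 points | 0.50 SD | 0.200 SD | 0.353 | 0.486 |

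The result runs from negligible to serious depending wholly on the assumptions. For the same bias, a larger trial makes the inflation greater, because the SE shrinks and the bias does not.

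**The case against.** The strongest reply is that nothing readable shows the cue to be informative. The sensory effects are named as examples of events that need no inspection, not as events commoner on drug. Protocol 7.2 describes the placebo tablets as identical, and the summary of prior experience in Protocol 5.1.1 is blacked out. This stands, and it is why the range must start at zero.

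Second, the order is only a general one, no passage says that the rater takes adverse events, and Protocol 11.2.1 leaves further CAPS-5 conduct and training rules to separate material that may already keep the roles apart. Protocol 11.3.1 also asks for open, non-leading questions. These points lower the risk but do not remove it: Protocol 11.2 still calls for the specified order, and an open question does not stop a patient from volunteering a numb tongue. If the separate material covers the point, a cross-reference would close it.

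Third, reordering does little alone. The Week 2 call (Protocol 10.3) asks about oral events by name before any on-treatment CAPS-5, so by Week 12 a rater who also takes adverse events has had three earlier chances to learn the cue (Weeks 2, 4 and 8). This stands. Reordering withholds only what is new at the visit, so the remedy has to address the rater's role as well.

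A reader might also infer that the order biases the result toward the drug by 0.6 to 0.8 points. The documents do not support that. Those values need a difference of 30 to 40 percentage points, which for a 30–40% rate on drug means no such events on placebo, and a 2-point shift that has no source in the documents.

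**Conclusion.** The point holds as a cheap improvement to conduct. The order is as described at every post-dose visit with a CAPS-5, the protocol attaches importance to order, one site rater stays with the patient, and no readable safeguard keeps adverse-event information from that rater. Oral sensory events are anticipated in both documents.

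That the rater is in fact unblinded, or that the primary result is biased, is not established. Either would require the cue to be more frequent on drug and known to the rater; bias would also require that it move the score. The documents show none of these. The size cannot be estimated from them: it is zero with equal cue rates, and 0 to 0.8 CAPS-5 points under the assumed 0 to 40 percentage-point difference and 2-point shift.

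**What to change.** In Protocol 10.4, 10.5 and the 10.5.1 list for Day 11 onward, move the adverse-event item to after the CAPS-5. Add to Protocol 11.2.1 that the CAPS-5 rater does not review adverse-event information before completing the CAPS-5 for that visit and, where existing site staff allow, is not the person who takes adverse events at any visit, including the Week 2 call. At early termination this sentence also covers the step that records the reason for leaving.

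The oral examination, drug return and patient-completed scales need not move. Where scheduled, the examination already follows the CAPS-5, and moving the other two would not address a rater's guess.

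The cost is protocol and source-worksheet wording plus a short site memo. No visit or assessment is added, and adverse events are still collected at the same visit. Protection is partial: where one person holds both roles, cues from earlier visits remain. The CGI-S, a key secondary endpoint, is not protected, because Protocol 11.2.3 has it rated once all the assessments are available for review.
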